6.2 Waiver or Alteration of Authorization for the Uses and Disclosures of PHI

6.2.1 Access, use or disclosure of PHI representing no more than a minimal risk to the privacy of the individual

6.2.1.1 Plan to protect PHI from improper use or disclosure

Information is included in the “Confidentiality, Privacy and Data Management” section of this protocol.

6.2.1.2 Plan to destroy identifiers or a justification for retaining identifiers

Identifiers will be destroyed when the study has been completed and the results published.

6.2.2 Explanation for why the research could not practicably be conducted without access to and use of PHI

Information must be obtained either from the subject’s electronic medical record or self-reported physical history during recruitment to determine eligibility

6.2.3 Explanation for why the research could not practicably be conducted without the waiver or alteration of authorization

The waiver is requested only for recruitment to determine subject eligibility to ensure that no medical conditions that fall into the exclusion criteria are present and would thus preclude enrollment. This waiver will minimize the enrollment of subjects’ who may ultimately fail to meet the study inclusion/exclusion criteria.

6.3 Waiver or alteration of authorization statements of agreement

Protected health information obtained as part of this research will not be reused or disclosed to any other person or entity, except as required by law, for authorized oversight of the research study, or for other permitted uses and disclosures according to federal regulations.

The research team will collect only information essential to the study and in accord with the ‘Minimum Necessary’ standard (information reasonably necessary to accomplish the objectives of the research) per federal regulations.

Access to the information will be limited, to the greatest extent possible, within the research team. All disclosures or releases of identifiable information granted under this waiver will be accounted for and documented.

7.0 Study Design and Procedures

7.1 Study Design

This will be a randomized, blinded, controlled study.

This study will examine the effects of **single injections** of 0.5% ropivacaine with epinephrine or without epinephrine (20 ml of each) injected at ESP at the T5 vertebra level.

7.1.1 Randomization process

The subjects enrolled will be randomized into two groups (6 participants in each group) by a computer-generated randomization list using SAS software (SAS Institute, Cary, NC):

Randomization groups

1. Group RE will have 20mL of **0.5% Ropivacaine with epinephrine** injected at the left or right T5 transverse process.
2. Group R will have 20mL of **0.5% Ropivacaine without epinephrine** injected at the left or right T5 transverse process.

The randomization will be performed, using a sealed envelope technique, and will be stratified according to the side of the injections (either left or right) so that each arm will have equal number of left and right sided ESP blocks. This will be done by the investigational pharmacy while preparing the medications. All subjects, the anesthesiologist performing the procedure, the radiologist, and the research coordinator collecting the data will be blinded and will not be aware of the details of the injection and allocation of the participants. In the event that the patient has a concerning reaction or becomes unstable in any fashion, the patient will be immediately unblinded and removed from the study.

The conduct of the study will be as follows.

7.2 Study Procedures

7.2.1 Pre-Procedure Visit

This visit will take place at the Anesthesia Preoperative Evaluation Clinic (APEC) for pre-procedural evaluation.

At this visit:

- Consent to participate will be obtained from eligible patients
- Blood will be drawn for baseline creatinine level
- All subjects will be instructed to fast from solids for at least 6 hours prior to the study, with clear liquid permitted until 2 hours before the procedure.

The blood collected for the creatinine level will be taken in person by the research coordinator to the clinical lab of Hershey Medical center. The samples will be destroyed immediately after the required amount of blood is tested. The results of the creatinine test will be sent to PI and that will determine the inclusion of the subject in the study.

Day of Procedure - (n=12)

The procedure will be scheduled at least 24 hr. after the pre-procedure visit. On the day of the procedure, the investigational pharmacy will prepare the syringe according to the randomization. The appropriate study medication will be picked up by the coordinator at the investigational pharmacy. The appearance of the syringe will be the same regardless of the medication that is inside. The study physician will use the randomization number as generated by investigational pharmacy to determine on which side to place the block and allocate a study number. Subjects and outcome assessors will be blinded to randomization allocation.

Study subjects will report to the Clinical Research Center (CRC) of Milton S. Hershey hospital on the day of their scheduled study procedure. Once they are checked in to CRC and ascertained that they followed fasting instructions, the female participants will be asked to take pregnancy test using a urine sample and a standardized pregnancy testing kit. Once the pregnancy test is determined to be negative, they will be considered to be a study participant. If pregnancy test is positive, they will be excluded from the study. Once the participant is included in to the study, an intravenous access and continuous monitoring of vital signs (ECG, non-invasive blood pressure every 5 minutes, and pulse oximetry) will be established. 3 ml of blood will be obtained from the Intravenous line already placed in the subject prior to performing the block. These samples will be repeated at 20, 40, 60, 90, 120, and 240 minutes after completion of the injection of active drug. A member of the research team will manually transport the appropriately-

labeled blood collection tube to a storage freezer in the Perioperative Genomics Laboratory (C2813, C2848) during the transport, blood samples will be placed in Category A sealed triple packaging. During transport, the specimen tubes will be placed in splash-proof and leak-proof containers. These primary containers are placed inside of secondary containers which will be sealed. The blood samples will be processed and analyzed for ropivacaine level using HPLC at genomic laboratory of department of Anesthesia, Hershey medical center at a later date. The results of the level of the ropivacaine level will be used for analysis of the results for the study. The subjects will not receive the results of these tests. However, if any of the subjects if specifically request for the results of these test that will be given to them. The blood samples will be immediately destroyed after the results of the ropivacaine conc. in the samples is obtained. The additional blood from samples, if any, will be destroyed.

The subject will be placed in a sitting position, the skin over their upper back will be disinfected with chlorhexidine 2%, and the tip of the T5 transverse process on one side will be identified using a low-frequency curvilinear ultrasound transducer (Sonosite, Bethesda, USA) placed in a longitudinal parasagittal orientation as previously described. [4] The skin over the needle insertion site will be anesthetized with 2ml of lidocaine 1% conc. for patient comfort. A 22-gauge 10cm Tuohy needle (Stimuplex, BBraun, and Bethlehem, USA) will be inserted in-plane with the ultrasound beam to contact the T5 transverse process. One ml of 0.9% normal saline will be injected to confirm correct needle tip placement separating the ESP from transverse process, as evidenced by visible linear fluid spread deep to the erector spinae muscle. Injection of the specific volume and type of fluid according to the randomization group (see above) will then take place. MRI part of study stopped May 2023. After the completion of the assigned injection they will be transported to the MRI suite at the MRI core facility on the Hershey campus in a wheel chair. The subject will undergo two MRI's to determine the spread of the anesthetic. These will take place at approximately 30 and 90 minutes following the completion of the assigned block.

Following the Block injection (completion of the MRI data May 2023), the subjects will be allowed to sit, stand or lay down for the remainder of the study. Continuous monitoring and recording of vital signs will take place as, blood pressure and heart rate will be measured every 5 minutes, starting prior to performing the block, till 60 minutes after the block is performed and every 15 minutes thereafter for the duration of the study. A member of the research team blinded to the randomization allocation will perform a sensory assessment for loss of sensation to cold using ethanol on the skin at 20, 60, 120, 240, and 360 mins after the injection of active drug. The extent of sensory loss to cold will be marked on the body using a water-soluble color marker each time and will be photographed each time interval. A binary scoring system will be used for both assessments: 1 = reduced sensation; 2 = normal sensation.

Once the final sensory assessment has been completed (360 minutes following block), the subject will remain for an additional 30 minutes of observation. The intravenous cannula will be removed and the subject will then be discharged to return home. The subjects will be discharged from the research facility with a note to inform the PI or Research coordinator if they feel anything different or abnormal. The subject should not drive for 24 h after receiving the block, and will need to have someone to drive them home after the procedure.

7.3

Duration of Participation

It will take three days to complete this research study. For two consecutive days following the procedure they will be asked to participate in a follow-up phone call to discuss how they are feeling. The script for the follow-up phone call is attached.

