19.0 Adverse Event Reporting

20.0 Study Monitoring, Auditing and Inspecting

21.0 Future Undetermined Research: Data and Specimen Banking

22.0 References

1.0 Objectives

1.1 Study Objectives

The **primary objectives** of this study are to define the extent of dermatomal anesthesia and anatomical spread of injectate (as defined by MRI imaging) that is provided by an ESP block at the T5 level, using twenty milliliters of 0.5% ropivacaine. MRI data will not be collected after May 2023

The **secondary objectives** include: 1) the measurement of changes in hemodynamic parameters associated with the ESP block, 2) the duration of sensory effects provided by ropivacaine with or without epinephrine, 3) the venous plasma concentration of ropivacaine at various time intervals after completion of the ESP block.

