1.2 Primary Study Endpoints

Outcomes to be assessed

1. Extent of dermatomal sensory loss
2. Duration of sensory loss
3. Anatomical extent of injectate spread using MRI imaging. MRI data will not be collected after May 2023
4. Venous plasma concentration of ropivacaine at periodic time intervals

We are comparing these outcomes between

1. 20ml ropivacaine 0.5% with epinephrine vs no epinephrine

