2.3 Study Rationale

At present, no systematic investigation has been published that describes first, the spread of injectate following the ESP block in live human subjects; second, the extent of sensory blockade that can be reliably expected; and third, the pharmacokinetics of local anesthetic injected into this location. It is also unknown what effect additives such as epinephrine, might have on these parameters. Epinephrine is commonly used for erector spinae plane blocks (ESP) or similar peripheral fascial plane injections to produce local vasoconstriction in order to prolong the action of the ropivacaine. The current evidence for the mechanism of action and efficacy of the ESP block in providing sensory blockade of the thorax comes from cadaveric studies and small patient case series.[4-6] For this potentially valuable regional anesthesia technique to be adopted more widely in clinical practice, it is essential to determine, with more precision, the mechanism of action in live human subjects, and the extent of sensory blockade that can be reliably achieved

with clinically significant volumes of injectate boluses. Local anesthetic systemic toxicity, although rare, is always a concern in regional anesthesia and it is, therefore, also important from a safety perspective to determine the pharmacokinetics associated with the ESP block, so as to provide appropriate guidelines for maximum dose, volume and concentration of local anesthetic to be injected. In addition, this knowledge will provide baseline data from which to embark upon comparative studies with other more established techniques for regional anesthesia of the thorax, such as thoracic epidural or thoracic paravertebral blocks. A volunteer study in non-anesthetized subjects offers the most controlled setting to study these factors, as it eliminates the confounding effects of concomitant analgesic and anesthetic medications, surgical trauma, and patient co-morbidities.

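### Duration of sensory loss is known only to within 120 minutes after the 120-minute reading and is right-censored at 360 minutes; three extra cold tests and a censoring rule would recover much of the lost precision.

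*Combined protocol and SAP*

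**What the plan says.** Section 1.2 lists "Duration of sensory loss" as item 2 of the primary endpoints, compared with and without epinephrine. Section 1.1 places "the duration of sensory effects provided by ropivacaine with or without epinephrine" among the secondary objectives. Section 2.3 says epinephrine is used "in order to prolong the action of the ropivacaine", but gives no size in minutes.

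The measurement in section 7.2.1 is a "sensory assessment for loss of sensation to cold using ethanol on the skin at 20, 60, 120, 240, and 360 mins" after injection, and the table in section 10.4 shows the same times. The scale is two-valued: "A binary scoring system will be used for both assessments: 1 = reduced sensation; 2 = normal sensation". Spatial extent is also kept: "The extent of sensory loss to cold will be marked on the body using a water-soluble color marker each time", with a photograph. The sensory readings then end: "Once the final sensory assessment has been completed (360 minutes following block), the subject will remain for an additional 30 minutes of observation". The 10.4 table has vital signs every 15 minutes from 60 to 360 minutes, including 180 and 300. Section 7.3 adds phone calls on the two following days about how subjects feel, using a script that is attached but not part of the document reviewed.

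Section 7.1.1 randomizes "two groups (6 participants in each group"). Section 8.2 calls the study a descriptive pilot for a larger trial. Section 8.3 names a test for MRI measurements and a chi-squared test for dermatomal anesthesia. No section defines duration or names a method for it.

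**The concern.** The one comparison in the trial is epinephrine against none, and the expected effect is a longer block. The readings that would show this are 120 minutes apart from the 120-minute reading onwards, and then they stop. Subjects who recover at 125 and 235 minutes yield the same data. A subject still blocked at 360 minutes yields only a lower bound.

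Two things are at stake. The first is precision: with 6 per arm, heavy ties leave little to separate the groups or to describe the spread. The second is truncation: if epinephrine works, its arm will more often pass the last reading, so the data thin out on the side where the effect lies. A larger trial planned from these results needs a usable mean, SD and difference in duration, and all three depend on the reading times.

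**Working it through.** The plan states no power or sample-size figure for duration, so there is none to reproduce. The check is of the reading grid.

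**Inputs from the protocol.** Readings at 20, 60, 120, 240 and 360 minutes (7.2.1, 10.4), so gaps of 40, 60, 120 and 120 minutes. Six per arm (7.1.1). No alpha, SD, block duration or effect size is given.

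**Assumptions, not from the documents.** Normal recovery times, with plain-arm mean 180–420 minutes, SD 30–90 and epinephrine effect 30–120. Two-sided 0.05 is used only as a common yardstick.

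**1. Does a shift cross a reading?** For a shift d below the 120-minute gap, with recovery evenly spread over the gap, the chance is d/120: 30/120 = 25%, 60/120 = 50%, 90/120 = 75%.

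**2. Variance added by grouping.** A gap h adds about h²/12. For h = 120 this is 14,400/12 = 1,200, an SD of 34.6 minutes. For h = 60 it is 3,600/12 = 300, an SD of 17.3 minutes. Relative efficiency is SD²/(SD² + h²/12):

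| SD (min) | 120-min gaps | 60-min gaps |
|---|---|---|
| 30 | 900/2,100 = 43% | 900/1,200 = 75% |
| 45 | 2,025/3,225 = 63% | 2,025/2,325 = 87% |
| 60 | 3,600/4,800 = 75% | 3,600/3,900 = 92% |
| 90 | 8,100/9,300 = 87% | 8,100/8,400 = 96% |

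This covers grouping only, not the stop at 360.

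**3. Simulation of 6 against 6.** Exact permutation rank-sum test, 2,500 to 3,000 trials per scenario. Recovery is rounded up to the next reading, and subjects still blocked at the last reading are tied at the top. Ranges span repeated independent runs.

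| Plain mean, effect, SD (min) | Exact times | Planned grid | 180, 300, 390 added |
|---|---|---|---|
| 240, +90, 45 | 83–84% | 31–34% | 71–72% |
| 240, +60, 60 | 28–29% | 10–12% | 22–23% |
| 300, +120, 60 | 82–84% | 46–48% | 74–75% |
| 360, +120, 75 | 64% | 8–9% | 24–26% |

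**4. Effect of the stop at 360.** In the last row the epinephrine arm has mean 480, and 120/75 = 1.6 SDs puts about 94% of it past 360. At 390 minutes, 90/75 = 1.2 SDs still leaves about 88% blocked, which is why the added readings help little there. With plain mean 420 and SD 60, 84% of the plain arm is already past 360, and a 120-minute effect has power 83% with exact times and 0% on the planned grid.

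**5. Bias under one scoring rule.** Suppose recovery is scored at the next reading and subjects still blocked are scored 360. A true +90 (mean 240, SD 45) then averages 58 minutes, a true +120 (mean 300, SD 60) averages 19, and a true +120 (mean 360, SD 75) averages 7.

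**6. The contrary result.** With interval midpoints (420 for those still blocked at 360), SD 60 and plain mean 180–240, a true +60 averages 57–59 minutes. Grouping alone barely biases the mean there.

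**The case against.** The strongest reply is that power is the wrong yardstick. Section 8.2 promises descriptive results, and no test or alpha is set for duration. That is right, so the power figures are used only to rank reading schedules by the information they carry. The gain from closer readings also applies to a descriptive estimate.

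A reader might infer that any effect shorter than 120 minutes is lost. The figures do not support that. At SD 60 or more with recovery well before 360 minutes, grouping efficiency is at least 75% and the mean difference is nearly kept. The marked and photographed extent also records how the block regresses, although it cannot supply an end time after 360. At SD 60–90, a 60-minute effect has power of only 15–31% even with perfect timing, so six per arm is then itself a severe limit.

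A reader might also take it as given that the block wears off between 120 and 360 minutes, or that the estimate is biased towards zero. The documents give no block duration, and the bias in step 5 arises only if still-blocked subjects are scored as 360. The plan does not say they will be; it is silent. Nor can one say that the phone calls ignore recovery, because the script was not available.

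Finally, the 390-minute reading gives limited help when recovery is late, and recalled return of feeling is a different measure from a blinded cold test. Both points stand, and the fix allows for them.

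**Conclusion.** The point holds as one of precision and censoring. After the 120-minute reading, duration is known only to within 120 minutes, and it is right-censored at 360. That follows directly from sections 7.2.1 and 10.4. It matters because section 1.2 lists duration as a primary endpoint while section 8.3 gives no method for it.

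The size depends on assumed recovery times. Across the scenarios tabulated, power falls from 28–84% with exact times to 8–48% on the planned grid, and the added readings bring it to 22–75%. The loss is worst when recovery times cluster tightly or fall near or beyond 360 minutes, and mild when they are spread widely and fall well before 360. The documents do not say which case applies. The change is worth making because it is cheap and improves precision even if duration is only described.

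**What to change.** **Readings.** In section 7.2 and the 10.4 table, add the same blinded ethanol cold test at 180 and 300 minutes, which are already vital-sign times, and at 390 minutes, the end of the planned observation. The gaps after 120 minutes become 60 minutes, with a last gap of 30.

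**Definition and analysis.** State in section 8.3 that duration is the interval between the last reduced and the first normal reading, right-censored if sensation is still reduced at the last reading. Describe and compare it with a method that respects interval and right censoring. Do not score censored subjects as 360.

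**Follow-up call.** If the script does not already ask, ask subjects still blocked at discharge when sensation returned. Report this as a supportive, separately labelled measure, not merged with the cold-test data.

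**Cost.** Three short cold tests per subject by the same assessor, possibly one question in an existing call, and a small amendment. The May 2023 MRI stop suggests that some subjects may already have been studied on the present schedule. The reading grids would then be mixed and the gain smaller than simulated, but an interval-censored analysis accommodates this.

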10.4 Frequency of data collection

See table below

Frequency of data collection, including when safety data collection starts								
		Conse nt	Placeme nt of IV	Collecti on of blood samples	MRI Remov e May 2023	Monitori ng of Vitals	Phon e calls	Senso ry Evals
	Pre Procedure Visit	X		X				
The day of Procedure	On Arrival		X	X		X		
	5mts					X		
	10					X		
	15					X		
	20			X		X		X
	25					X		
	30				X	X		
	35					X		
	40			X		X		
	45					X		
	50					X		
	55					X		
	60			X		X		X
	75					X		
	90			X	X	X		
	105					X		
	120			X		X		X
	135					X		
	150					X		
	165					X		
	180					X		
	195					X		
	210					X		
	225					X		

	240			X		X		X
	255					X		
	270					X		
	285					X		
	300					X		
	315					X		
	330					X		
	345					X		
	360					X		X
	Post Procedure Day 1						X	
	Post Procedure Day 2						X	

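### The sensory score cannot separate absent from reduced cold sensation, so extent and duration may be overstated if reported as anesthesia

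*Combined protocol and SAP*

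**What the plan says.** All references are to the combined protocol and SAP.

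- Section 1.1 sets the primary objective: to "define the extent of dermatomal anesthesia and anatomical spread of injectate". Section 8.3 again names dermatomal anesthesia as the variable for the chi-square test.
- Section 1.2 lists the endpoint in different words, "Extent of dermatomal sensory loss", and makes the duration of that loss a primary endpoint as well.
- Section 7.2.1 (the day-of-procedure text sits under this heading) describes a blinded "sensory assessment for loss of sensation to cold using ethanol on the skin at 20, 60, 120, 240, and 360 mins" after injection. On recording it says: "The extent of sensory loss to cold will be marked on the body using a water-soluble color marker each time". Photographs are taken at each time. The scale follows: "A binary scoring system will be used for both assessments: 1 = reduced sensation; 2 = normal sensation".
- The schedule table in section 10.4 marks sensory evaluations at the same five times, with none at the pre-procedure visit or on arrival.
- On preparation for the block, section 7.2.1 says: "The skin over the needle insertion site will be anesthetized with 2ml of lidocaine 1% conc. for patient comfort". No section says how that skin is treated when the map is drawn.

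**The concern.** The objective and the analysis speak of anesthesia, but the only abnormal level on the scale is reduced. An area where cold is slightly dulled and an area where it is not felt at all receive the same code. The distinction is lost when the data are collected, and no later analysis can restore it.

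Reduced is also a comparative judgment, and the plan names nothing to compare with. There is no map before the block and no instruction to use the untreated side. Ropivacaine samples and vital signs do have pre-block values; the sensory outcome does not.

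This matters because the absolute figures are themselves results. Section 8.2 calls the study a pilot whose descriptive results will be used to plan a larger trial, and section 2.3 gives the reliably achievable extent of sensory blockade as a reason for doing it. MRI collection stopped in May 2023, so for anyone studied after that the sensory map is the only remaining measure of the primary objective. Duration has the same problem, because the end of anesthesia cannot be told from the end of partial dulling.

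**Working it through.** **Plan's own figure.** The only number to reproduce is the count of completers: 6 + 6 = 12, which agrees with section 8.1. No alpha, power, effect size or standard deviation is stated, so no sample-size formula applies. The rest is a comparison of passages plus illustrations on labelled assumptions.

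**Step 1, the scale.** Let A be the number of segments with absent cold sensation and R the number with reduced sensation only. Both are scored 1, so recorded extent = A + R, and the ratio to the absent area is (A + R)/A. The documents give neither A nor R. With assumed values:

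- A = 2, R = 0, 2, 4: 2/2 = 1.0, 4/2 = 2.0, 6/2 = 3.0
- A = 4, R = 0, 2, 4: 4/4 = 1.0, 6/4 = 1.5, 8/4 = 2.0
- A = 6, R = 0, 2, 4: 6/6 = 1.0, 8/6 = 1.33, 10/6 = 1.67

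The ratio is 1.0 whenever no segment is merely reduced. It is an overstatement only if the result is read as anesthesia.

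Duration works the same way. Suppose a segment is absent at 120 minutes, reduced at 240 and normal at 360. It is scored 1 up to 240 minutes, although absence was last present at 120. If it goes straight from absent to normal between two tests, the two durations coincide.

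**Step 2, no pre-block map.** Assume 12 segments (T1 to T12) are tested, k are truly reduced, and an unaffected segment is wrongly called reduced with probability f. Extra segments = f × (12 − k).

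- f = 0: 0 extra
- f = 0.05, k = 4 and 8: 0.05 × 8 = 0.4 and 0.05 × 4 = 0.2
- f = 0.10, k = 4 and 8: 0.10 × 8 = 0.8 and 0.10 × 4 = 0.4

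The range is 0 to 0.8 segments. Section 3.2 excludes people with neurological deficits, so a small value is more likely.

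**Step 3, lidocaine at the needle site.** It adds extent only where the block spares that skin (probability q) and the patch is read as w whole segments. Extra segments = q × w.

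- q = 0: 0 extra
- q = 0.5, w = 1: 0.5
- q = 0.5, w = 3: 1.5

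The range is 0 to 1.5 segments. Every subject receives the lidocaine, so with equal q and w in both arms the expected difference between arms is q × w − q × w = 0. The documents do not say how long it affects cold testing, so any effect at the early assessments is itself an assumption.

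**The case against.** The endpoint in section 1.2 is sensory loss, not anesthesia, and reduced versus normal cold sensation is a measurable outcome in its own right. Aligning the wording would cure much of the mismatch. The scale, the missing baseline and the lidocaine are the same in both arms and the assessor is blinded, so no bias in the epinephrine comparison is shown. The subjects are healthy volunteers, and the block is one-sided, so an untreated side is there to compare with. The extent is outlined and photographed, so an isolated patch at the needle site could be recognized and set aside at analysis.

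All of this stands, and it limits the point to the descriptive estimates. It does not remove the mismatch: section 1.1 and section 8.3 still say anesthesia, the plan does not tell the assessor to use the untreated side, and photographs of a single outline cannot show which areas inside it had no sensation.

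Two stronger readings are tempting. A reader might infer that extent is in fact overstated; nothing in the documents shows this. A reader might also count the lidocaine skin as one false dermatome on top of a true 3 to 6, an overstatement of 1/6 = 17% to 1/3 = 33%. That requires the block to spare the skin at the needle site of a T5 injection and a local patch to be read as a whole dermatome. If the block already covers that segment, the excess is 0%.

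**Conclusion.** The point holds as a mismatch between objective and measurement. As written, the plan records reduced cold sensation and cannot identify anesthesia within it. Extent and duration may therefore be overstated if reported as anesthesia. The size cannot be derived from the documents and may be zero; the ratios of 1.0 to 3.0 above rest entirely on assumed counts of absent and reduced segments.

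The missing pre-block map is a secondary gap, probably with a small effect in this population. The lidocaine site is minor: it could matter for a failed or patchy block at the early assessments, but it is common to both arms. The documents do not support calling the sensory outcome uninformative, since reduced cold sensation can be mapped and reported under that name. This is a cheap improvement to a descriptive pilot, not a defect that invalidates it.

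**What to change.** For remaining subjects:

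1. Score each dermatome as absent, reduced or normal.
2. Do one cold map before the block, by the same assessor, and add it to the section 10.4 table.
3. Use the untreated side as the reference at every time point.
4. Flag an isolated patch around the needle site, so that it is not counted as a blocked dermatome.
5. Report extent and duration twice: for absent sensation, and for absent or reduced sensation.

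For subjects already studied, report only the combined extent and label it reduced cold sensation, not anesthesia. First confirm that the outlines were drawn at the edge of reduced sensation, because section 7.2.1 describes marking loss but scores reduction.

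In the same edit, clarify the scoring sentence in section 7.2.1: it refers to two assessments, but only cold testing is described.

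The cost is one extra code and one map of a few minutes per subject. The drawback is that the absent-sensation extent will exist only for subjects studied after the change. The documents do not say how many of the 12 that is; the combined extent remains the one measure available for all of them.
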